2.6.5 Specimen Collection and Management

Specimen Collection / Documentation: A maximum of 34 ml of blood for experimental research studies and endpoint assays will be obtained pretreatment, and at weeks 6, 12, 18, and 24 after the start of therapy. The peripheral blood will be processed at the site of collection by centrifugation to separate mononuclear cells, plasma, and sera, which will be aliquoted and frozen (at -20° or below) until shipment to the CCC in batches. Subsequent assays will be conducted in the laboratory of CCC investigators or their colleagues, in compliance with IRB approvals.

Each research sample will be labeled with the subject's unique identifier, sample date, and sample collection time. The code number and date on which the specimen is frozen, all other information about the specimen, and subsequent processing will be entered on a specimen processing worksheet.

Covariate information, e.g., concomitant medications, laboratory values, etc., will be obtained at each time point.

Specimen Handling and Labeling (De-Identification)

All research specimens and all records associated with the samples will be labeled only with a unique code that links to the trial data, but contains no personal identifiers. The information linking these code numbers to the corresponding subject's identity will be kept in a secure location in the PI's office at each participating center, and will not be available to staff managing samples at the research laboratories.

Specimen Management and Storage: Specimens in excess of immediate assay requirements may be stored indefinitely in a secured freezer under the control of the responsible PI. The coding information linking patient identifiers to the stored samples will be maintained in a locked, secure area that will be accessible only to the study investigator. Subjects may request to have their samples destroyed at any time. These samples will be destroyed immediately upon receipt of the subjects' written request to do so.

Restrictions to Direct Access of Specimens: Specimens will be kept in the responsible study investigators' laboratories indefinitely and will be under the control of the PI. Other personnel not involved with the management or operations of the study are not permitted direct access to the specimens.

2.7 STUDY ENDPOINTS

2.7.1 Primary Efficacy Endpoint:

The primary endpoint of this trial will be treatment effects of GKT137831 on plasma levels of *o,o'*-dityrosine, measured by mass spectroscopy pretreatment and at six-week intervals, in comparisons to effects of placebo alone.

O,o'-dityrosine is a mechanistic surrogate biomarker of oxidative stress. This metabolite is synthesized by myo-fibroblasts in fibroblastic foci, and is associated with cellular injury and ECM cross-linking (Secs. 1.3.5., and 1.3.6.). Levels of *o,o'-dityrosine* are increased in IPF patients (Sec. 1.3.7.) and were significantly decreased by GKT137831 administration in a murine model of fibrotic lung injury (Sec. 1.3.9.).

We hypothesize plasma levels of *o,o'*-dityrosine in IPF participants will be reduced by NOX inhibition with GKT137831, reflecting beneficial effects of the experimental drug on fibrosis (Sec. 1.3.8).

2.7.2. Secondary Efficacy End-Points:

Secondary endpoints are: (a) collagen degradation products (e.g.C1M), measured in sera by ELISA; (b) forced vital capacity (FVC); and (c) six-minute walk distance (6MWD) comparing baseline and values at 24 weeks; and (e) adverse events (AE) that occur anytime during the duration of the trial.

a) C1M: Circulating concentrations of collagen digest fragments (e.g., C1M) are reflective of ECM turnover, and increased levels discriminate IPF patients vs. controls, and are prognostic of disease activity and outcome (Sec. 1.3.10.). C1M will be measured by competitive ELISA in serum specimens collected by phlebotomy at visits that occur every 6 weeks in all patients. The assays will be performed at Nordic Biosciences (Herlev, Denmark), as previously described (16). We hypothesize GKT137831 treatment will result in decreased ECM turnover and reductions of sera C1M levels, in comparison to placebo effects.

b) and c) FVC and 6MWD: This is a Phase IIb study and is likely underpowered for rigorous evaluation of drug effects on clinical endpoints, such as FVC changes and/or 6MWD over time. Nonetheless, measures and comparisons of these parameters will enable us to detect striking drug efficacy, and will likely be informative with respect to power calculations for later, more definitive efficacy trials. FVC is a measure of pulmonary restriction (in turn, a function of the underlying lung fibrosis). 6MWD are simple, inexpensive, reproducible measures of global cardiopulmonary function. Values for 6MWD can be obtained in all patients, even those who are immobile (e.g., value = 0). Measures of FVC and 6MWD will be performed per ATS/ERS guidelines. These tests are standard of practice (SOP) in our IPF clinics.

2.7.3. Safety Endpoints:

Adverse events: Adverse events (AE) that occur anytime during participation in this study will be recorded and compared. The NCI Common Toxicity Criteria Scale will be used to define grades (severity) of adverse events and toxicities. An AE is defined as any untoward medical occurrence in a subject, regardless of its relationship to these treatments. Toxicity is an adverse event with a direct relationship to the study drug. All toxicities are AE, but not all AE are toxicities. Computer data entry (and case report forms- [CRF]) will require responses to all adverse events, with a particular focus on infections (including location and organism), and metabolic perturbations (e.g., cardiac, liver, bone marrow, or thyroid abnormalities) hyperglycemia, hypotension, etc.). Recording all AEs in pre-specified checklists (and free text entries), will guard against unintended bias in this unblinded trial. We hypothesize GKT137831 will be safe in this population, and will not be associated with an increased number or severity of AE in comparison to placebo.

2.7.4. Pharmacokinetic endpoints:

Plasma concentrations of GKT137831 and its main phase 1 metabolite, GKT138184. The plasma concentrations will be subjected to population PK analysis to estimate population PK parameters such as clearance and volume of distribution and associated inter-individual variability (IIV), and to determine predictors of IIV. PK-PD analysis will be carried out using the primary endpoint and selected secondary endpoints in order to explore any potential PK- PD relationships.

2.7.5 Additional Studies That are Not Formal Endpoints

Quality of Life (QoL) Measures: Patients will complete a King's Brief Interstitial Lung Disease health status questionnaire (K-BILD) at baseline and study conclusion (24 weeks). This instrument was developed for and validated in patients with interstitial lung disease, is brief, simple to administer, measures health status in three domains, and is reproducible.⁴⁶

2.8 DATA ANALYSES AND POWER ANALYSES

2.8.1. Data analyses: Baseline demographic and clinical data of participants will be summarized using means (with standard deviations) and medians (with inter-quartile ranges) for continuous variables, and counts and percentages for discrete variables, stratified by treatment group. Differences between groups (to examine the randomization effectiveness), will be assessed by t-tests, or by Fisher's exact test for discrete data. Analyses will follow intention to treat principles, with the last observed outcome over all time points being used as the primary measure for a given variable. Multiple imputation will be used based on subject characteristics to assess the obvious issues, with last observations carried forward in these analyses. Trajectories over time, for a given patient and outcome measure, will be displayed via line graphs, and assessments conducted using generalized linear models on the repeated time points. Comparisons between the treatment arms of circulating o,o'-dityrosine levels at various time points will be made using these repeated measures techniques. Transformations of these tests may be needed, such as velocities, if many individuals are unable to complete the entire protocol.

2.8.2. Power analyses: The sample size of 60 for this clinical trial (equally divided between experimental and placebo arms) is based on exposing a minimum number of patients to risks of experimental therapy, while still obtaining useful information. We previously found that o,o'-dityrosine levels ($\mu\text{mol/mol}$ tyrosine) in IPF patients ($n = 32$) were 8.51, with a standard deviation (SD) of 5.30, compared to mean and SD of 0.47 ± 0.45 in normal controls (15). Assuming o,o'-dityrosine levels are reduced in the experimental arm subjects by 50% of the difference between untreated IPF and normals (e.g., to $4.02 \mu\text{mol/mol}$ tyrosine), with a SD of 5.3 we will be able to reject the null hypothesis that the population means of the experimental and control groups are equal with probability (power) 0.82, using an unpaired, two-way t-test. The Type I error probability associated with this test of this null hypothesis is 0.05. The 50% reduction is well within ranges in which ROS and fibrosis markers are decreased by GKT137831 in other models (Sec. 1.3.9., and 8-11).

Moreover, we have 0.8 power to detect a treatment effect **within the 30 experimental arm subjects**, using paired intragroup testing, if o,o'-dityrosine levels decrease from baseline levels by merely $1.4 \mu\text{M/mol}$ tyrosine or more during GKT137831 therapy.

The characteristics of this trial, which is double-blinded, involves overlapping roles of many personnel at many centers, employs an independent and expert DCC (that routinely does QC checks and validations) for data collection and analyses, and uses an endpoint that is determined independently by blinded experimental lab investigators working with deidentified specimens, **ensure a high degree of transparency and rigor.**

2.8.3. Interim Analysis:

Interim efficacy analysis is not warranted, since the primary study endpoint is a laboratory measure of the plasma level of o,o'-dityrosine, a surrogate biomarker of oxidative stress, to

determine GKT137831 treatment effects. The DCC will tabulate AE and the DSMB will monitor AE in the respective trial arms.

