Study Aims:	
 1. To conduct a proof-of-concept, mechanistically-driven, double-blinded, placebo-controlled trial, to examine effects of GKT137831 administration on a surrogate measure of oxidative stress and pulmonary injury in IPF patients. 2. To determine effects of GKT137831 administration in IPF patients, compared to placebo, on four secondary efficacy endpoints: (a) levels of collagen degradation product, C1M, measured in sera by ELISA; (b) and forced vital capacity (FVC) at baseline and 24 weeks. Also (c) six-minute walk distances (6MWD) will be measured at baseline and 24 weeks; and (d) adverse events (AE) will be recorded throughout the subject's participation in this study.

Study Design:	
Following screening assessments, IPF patients who meet all inclusion/exclusion criteria will be randomly assigned to receive one of the following treatments in a ratio of 1:1:
 
 • Arm A (n=30) – GKT137831 Treatment: GKT137831 will be administered orally, at a dose of 400 mg bid, for a total of 24 weeks. • Arm B (n=30) - Placebo Treatment: Arm B subjects will receive matching placebo for the same duration. 
Participants will be followed in face-to-face visits with trial personnel every 6 weeks for 24 weeks to assess drug effects and monitor safety during their treatments, and by phone surveillances one month thereafter.

Planned Sample Size:	A total of 60 subjects will be enrolled in this multi-center trial from among IPF patients at 5 participating medical centers.
Duration of Study:	Up to a maximum of 32 weeks, including screening (4 weeks maximum), drug administration for 24 weeks, and then a final surveillance phone contact 4 weeks later.
Inclusion Criteria:	
 1) Age between 40-85 years old. 2) A diagnosis of IPF that fulfills current ATS/ERS Consensus Criteria (1). 3) IPF duration <10 years, based on the date of definitive diagnosis. 4) Ability and willingness to give informed consent and adhere to study requirements. 5) Ratio of forced expiratory volume in 1 second to forced vital capacity (FEV₁/FVC) >70% of predicted values

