	
15) Systemically administered potent CYP3A4 inhibitors or inducers are prohibited during the 24-week treatment period.
 
Inhibitors include: boceprevir, cobicistat, conivaptan, ritonavir, itraconazole, ketoconazole, telaprevir, troleandomycin, voriconazole, clarithromycin, diltiazem, idelalisib, nefazodone, nelfinavir.
 
Inducers include carbamazepine, enzalutamide, mitotane, phenytoin, rifampin.
 
See also: https://www.fda.gov/drugs/drug-interactions-labeling/drug-development-and-drug-interactions-table-substrates-inhibitors-and-inducers#table3-2

Study Endpoints:	
 • Primary efficacy endpoint: The primary efficacy endpoint is change in plasma o,o'-dityrosine, as determined by mass spectroscopy, from baseline to Week 24. • Secondary efficacy endpoints: Secondary efficacy endpoints are: (a) collagen degradation products, (e.g., C1M), measured in sera by ELISA; (b) forced vital capacity (FVC); and (c) six-minute walk distance (6MWD) comparing baseline to values at 24 weeks.
	
 • Safety: Adverse events (AEs) that occur anytime during the duration of the trial. Clinical laboratory evaluations will occur at Screening, baseline/Day 1 and Weeks 6, 12, 18, and 24. Urinalysis will be performed at Screening, baseline/Day 1 and Weeks 6, 12, 18, and 24. Pulse rate, SBP and DBP are recorded at Screening, baseline/Day 1 and Weeks 6, 12, 18, and 24. Body weight at Screening, baseline/Day 1 and Weeks 6, 12, 18, and 24. 12-lead ECG at Screening, baseline/Day 1 and Weeks 6, 12, 18, and 24.
	
 • Pharmacokinetics (PK): Plasma concentrations of GKT137831 and its main phase 1 metabolite, GKT138184. The plasma concentrations will be subjected to population PK analysis to estimate population PK parameters such as clearance and volume of distribution and associated inter-individual variability (IIV), and to determine predictors of IIV. PK-PD analysis will be carried out using the primary endpoint and selected secondary endpoints in order to explore any potential PK-PD relationships.

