1.2 SPECIFIC AIMS

Central Hypothesis: Our primary hypothesis is that treatment of IPF patients with the NOX1/4 inhibitor GKT137831 will reduce pulmonary oxidative injury, as ascertained by reductions in plasma levels of a mechanistic surrogate biomarker (*o,o'*-dityrosine). A corollary of this hypothesis is that treatments that reduce oxidative injury in these patients will have a favorable effect on the natural history of IPF.

The studies proposed here are primarily designed to determine the magnitude of the ROS metabolite reduction and further assess safety of GKT137831 in IPF patients. Nonetheless, we hope that experimental treatments may result in clinically-relevant beneficial effects, as determined by secondary endpoints that include preservation of forced vital capacities and ability to ambulate.

The Specific Aims of this Trial are:

1. To conduct a double-blinded, placebo-controlled Phase II clinical trial in 60 ambulatory IPF subjects at five major medical centers. Subjects will be randomized 1:1 to GKT137831 or matching placebo, and treated for six months. The primary endpoint of this trial will be treatment effects of the experimental drug on plasma levels of *o,o'*-dityrosine, measured by mass spectroscopy pretreatment and at six-week intervals.

*We hypothesize the experimental therapy will reduce plasma levels of *o,o'*-dityrosine, reflecting target engagement of the drug, and reductions of oxidative stress and injury.*

2. To determine the efficacy of GKT137831 therapy in IPF patients, compared to placebo, on four secondary endpoints, measured at baseline and at six-week intervals of: (a) collagen degradation product, C1M, measured in sera by ELISA; and (b) FVC; (c) and 6MWD at baseline and 24 weeks week intervals.

We hypothesize the experimental therapy will decrease circulating levels of C1M. Although the short-duration treatment in this Phase II clinical trial may not result in significant effects on the secondary clinical endpoints, the results of these studies will be critical for the design and power analyses of future GKT137831 Phase III trials. Moreover, this as-of-yet untested drug treatment for IPF may prove to be very effective, and these measures will enable us to detect an unprecedented benefit of this novel approach.

3. To assess the safety and tolerability of GKT137831 in patients with IPF. The incidence and severity of AEs, laboratory tests and ECG abnormalities will be assessed over the course of the trial.

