Informed Consent Modifications made on Jan. 26, 2020 to now become ICF v2.0 1/26/2020. Changes to the former ICF are delineated with yellow highlighting.

- 1) It is now explicitly stated herein that subjects will be notified regarding incidental or other clinically-significant lab abnormalities.
- 2) Clarification and correction that 6MWD tests will be made at 12 weeks, rather than 6 week intervals.

Protocol Modifications made on March 6, 2020 to now become Protocol v6.0 3/6/2020. Changes to the former Protocol are delineated with tracked changes. These changes were requested by the DSMB and are largely changes to phrases, corrections of typos or grammar. None of these changes represent a significant change of procedures or practices.

- 1) The date and version number were updated on header and Synopsis to current iteration v.6.0, March 6, 2020).
- 2) The wording of Interim Analysis (section 2.8.3) has been changed in accordance with DSMB suggestions. The context/meaning remains the same.
- 3) A phrase describing how the study population is at high risk in Section 5.7.2 has been deleted.

Informed Consent Modifications made on March. 6, 2020 to now become ICF v3.0 3/6/2020. These changes, delineated with tracked changes, were requested by the DSMB and are largely changes to phrases, corrections of typos or grammar. None of these changes represent a significant change of procedures or practices.

- 1) The words of the bulleted summary on page 1, "What should I know about this research", have been changed to be identical to another, near identical bulleted summary later in the ICF, to maintain consistency.
- 2) In various and multiple places (page 2 and several others) the definition of "placebo" and "randomization" have been reiterated.
- 3) The potential organizations that could potentially share private information has been streamlined to omit Genkotex (page 13).

PROTOCOL MODIFICATIONS: Made on August 1.0 to Version 6.0 (to now become V7.0)

- 1) Dates and protocol version numbers were changed throughout (to now become V7.0 August 1, 2020)
- 2) The interval PFTs (spirometry and DLCO) and 6MWD at 6, 12, and 18 weeks have been deleted. These tests instead will be performed at baseline and compared to values obtained at the conclusion of the study at week 24. This change was made in considerations of difficulting involved in obtaining these particular tests during the covid pandemic.

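### Last observation carried forward is the primary measure for each efficacy variable; FVC and 6MWD have no test between baseline and week 24, so a missing week-24 result is naturally read as no change

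*Combined protocol and SAP*

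**What the plan says.** Section 2.8.1 follows intention to treat, "with the last observed outcome over all time points being used as the primary measure for a given variable". It exempts no efficacy variable. The next sentence adds: "Multiple imputation will be used based on subject characteristics to assess the obvious issues, with last observations carried forward in these analyses". It gives no imputation model, names no variables beyond subject characteristics, and does not rank imputation against carry-forward. The same section plans repeated-measures models for trajectories and for comparing dityrosine between arms, again without saying which analysis is primary.

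The synopsis places "forced vital capacity (FVC) at baseline and 24 weeks" and, among the secondary endpoints, lists "c) six-minute walk distance (6MWD) comparing baseline to values at 24 weeks". Table 1 and the visit list in Sections 2.6.3 and 2.6.4 agree. The Section 10 entry for V7.0 explains why the interim tests went: "These tests instead will be performed at baseline and compared to values obtained at the conclusion of the study at week 24". The log records no matching change to the analysis section. Aim 2 in Section 1.2 still has secondary endpoints "measured at baseline and at six-week intervals of: (a) collagen degradation product, C1M" followed by FVC, which can be read as six-weekly FVC and conflicts with Table 1.

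On special values, Section 2.7.2 says: "Values for 6MWD can be obtained in all patients, even those who are immobile (e.g., value = 0". Death is not mentioned.

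For dityrosine, the synopsis defines the endpoint as a change, "as determined by mass spectroscopy, from baseline to Week 24". Sections 1.2 and 2.7.1 instead describe treatment effects on levels measured before treatment and every six weeks.

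**The concern.** A last-observation rule needs something informative to carry. When FVC and 6MWD had interim visits, a dropout would have contributed a week 6, 12 or 18 value. With those visits removed, the only earlier value is the baseline, and baseline minus baseline is zero. Section 1.3.1 describes IPF as relentlessly progressive, with a median survival of 3 to 4 years after diagnosis, so no change is a favourable score for someone who died or became too ill to attend.

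The 6MWD scoring is also inconsistent: a survivor who cannot walk scores 0 m, while a patient who dies keeps the baseline distance.

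Two things are at stake. The mean decline is pulled toward zero, and the pull is stronger in the arm with more missing data, so unequal dropout can create or hide a difference. Section 2.7.2 also intends these results to inform power calculations for later trials, so the distortion would carry into their design.

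**Working it through.** **The plan's own figure.** The only stated power is for dityrosine. With 30 per arm, a difference of 50% × (8.51 − 0.47) = 4.02, SD 5.3 and two-sided 0.05, the exact t calculation gives 0.823 against the stated 0.82. It makes no allowance for missing data. No effect size, SD or power is given for FVC or 6MWD, so what follows is illustration.

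**Inputs from the documents**
- Arm size: 30 (Section 2.8.2).
- Missing, lower figure: under 7%, from over 93% completing 24 weeks in the PBC trial (Section 1.3.12).
- Missing, higher figure: 39 of 44 completed in earlier IPF trials at one site (Section 4.1.2), so 5/44 = 11.4% did not.

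**Assumed:** completers' FVC decline of 100 mL where a figure in mL is needed; baseline 6MWD of 400 m; the dropout split of 20% versus 5%.

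**1. Patients affected per arm.** 30 × 0.07 = 2.1; 30 × 5/44 = 3.4.

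**2. Bias in one arm's mean.** Let m be the share missing, C the completers' mean change, and kC the true mean change in the missing.
- True mean = (1 − m)C + mkC.
- Carried-forward mean = (1 − m)C + m × 0 = (1 − m)C.
- Share of the decline lost = mk / (1 − m + mk).

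| m | k = 0.5 | k = 1 | k = 2 | k = 3 |
|---|---|---|---|---|
| 7% | 3.6% | 7.0% | 13.1% | 18.4% |
| 11.4% | 6.0% | 11.4% | 20.4% | 27.8% |

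For example, with m = 5/44 and k = 2: (10/44) / (39/44 + 10/44) = 10/49 = 20.4%.

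**3. Equal missingness in both arms, k = 1.** The difference between arms is multiplied by (1 − m): 0.93 or 0.89.

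**4. Unequal missingness, no drug effect.** If all patients decline by the same amount, the carried-forward difference is (missing share on active − missing share on placebo) × decline. With 20% versus 5% this is 0.15 × decline: 7.5, 15 or 22.5 mL for assumed declines of 50, 100 or 150 mL, in favour of the arm with more missing data.

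If completers lose 100 mL and the missing lose 200 mL:
- True means: active 0.80 × (−100) + 0.20 × (−200) = −120; placebo 0.95 × (−100) + 0.05 × (−200) = −105. The difference is −15 mL.
- Carried forward: −80 against −95. The difference is +15 mL.

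The sign reverses.

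**5. Death and 6MWD.** Scoring one death at the baseline distance rather than 0 m moves the arm mean by 400/30 = 13.3 m. The plan does not say which applies.

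**6. Dityrosine and C1M.** Samples are taken at weeks 6, 12, 18 and 24. A patient lost after week 6 contributes a week-6 value in place of week 24. Change is forced to zero only if every post-baseline sample is missing.

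**The case against.** The strongest reply is that the text speaks of the last observed outcome and never says that baseline counts as one. A patient with no post-baseline FVC might then have nothing to carry and would fall to the multiple imputation. That reading is possible, but the plan does not state it, and the imputation sentence itself mentions carry-forward.

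Other points stand and limit the finding:
- **Dityrosine.** Repeated-measures comparisons are already planned, and the endpoint is defined in two ways. The fair criticism is undefined precedence, not the absence of a suitable model.
- **Imputation.** A reader might infer that the imputation has no between-imputation variance and that standard errors are therefore too small. The sentence may equally describe imputation from subject characteristics run beside carry-forward, so this is not shown.
- **Scope.** A reader might extend the rule to every endpoint. Adverse events are among the listed secondary endpoints, and Section 6.7.2 says missing safety data will not be imputed.
- **Severity of the score.** A reader might say the sickest patients get the best possible result. Zero change is not the maximum, since FVC and 6MWD can improve, and survivors who cannot walk get the worst 6MWD value.
- **Amount missing.** The 39/44 figure pools trials of 12, 48 and 60 weeks. Section 4.1.2 also reports no loss through noncompliance among 30 patients in another IPF trial. Section 2.2 keeps patients who stop for adverse events under follow-up, and Section 2.6.1 allows assessment in hospital where feasible. These measures reduce missing data but cannot supply a test after death.
- **Chart values.** Section 2.2 lets standard-of-care results be used as research data, but does not say that they enter the endpoint.
- **Importance.** FVC and 6MWD are secondary, and Section 2.7.2 concedes that the trial is likely underpowered for them.

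**Conclusion.** The concern holds for FVC and 6MWD. The stated rule and the current schedule together score a missing week-24 test as no change on the natural reading, and death has no rule. At 7 to 11.4% missing, the mean decline is understated by about 7 to 11% if the missing resemble completers. This is not a lower bound: at half the completers' rate it is 3.6 to 6.0%, and at twice the rate 13.1 to 20.4%. V7.0 removed the interim tests because of pandemic difficulties, so not every missing test need reflect progression. The false benefit of 15% of the decline rests on the assumed 20% versus 5% split and on equal decline in all patients.

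For dityrosine and C1M the problem is milder: an early value can stand in for week 24. For dityrosine, the plan also leaves open whether carry-forward or the repeated-measures model is primary. The documents do not support the claim that the primary endpoint is forced to zero change.

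**What to change.** 1. In Section 2.8.1, delete the last observed outcome as the primary measure, and remove carry-forward from the multiple-imputation sentence.
2. **Dityrosine and C1M:** name the already planned repeated-measures model as the primary analysis for dityrosine and use it for C1M. Specify it as likelihood-based, using all post-baseline visits, adjusted for baseline, with the week-24 contrast. Reconcile the dityrosine endpoint wording in the synopsis with Sections 1.2 and 2.7.1.
3. **FVC and 6MWD:** use week-24 ANCOVA adjusted for baseline, with multiple imputation from observed baseline and interim data, and never with baseline carried forward. State the imputation model and its variables before unblinding.
4. **Death:** add a separate rank-based sensitivity analysis with death ranked worst. Keep it apart from the ANCOVA, because a mean difference in mL or metres and a ranking that includes death answer different questions. State whether the 0 m rule is limited to living patients who cannot walk.
5. Reconcile the leftover six-weekly FVC wording in Aim 2 (Section 1.2) with Table 1.

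The cost is revised wording, a little more analysis work and possibly slightly wider intervals. No new data or patients are needed.

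### The primary test is not uniquely pre-specified, so control of type I error at 0.05 is not assured

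*Combined protocol and SAP*

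**What the plan says.** Four places in the combined protocol and SAP bear on the test of the primary hypothesis.

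- **Synopsis, Study Endpoints.** The primary endpoint is change in plasma dityrosine, "as determined by mass spectroscopy, from baseline to Week 24".
- **Section 2.7.1.** The endpoint is the treatment effect on plasma levels, "measured by mass spectroscopy pretreatment and at six-week intervals, in comparisons to effects of placebo alone". No decisive visit is named. Aim 1 in section 1.2 is worded similarly.
- **Section 2.8.1.** The analysis follows intention to treat, "with the last observed outcome over all time points being used as the primary measure for a given variable". For dityrosine it adds: "Comparisons between the treatment arms of circulating o,o'-dityrosine levels at various time points will be made using these repeated measures techniques". It then allows a change: "Transformations of these tests may be needed, such as velocities, if many individuals are unable to complete the entire protocol".
- **Section 2.8.2.** The sample size is justified "with probability (power) 0.82, using an unpaired, two-way t-test", and "The Type I error probability associated with this test of this null hypothesis is 0.05". The section goes on to give a paired within-arm test its own power of 0.8.

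Section 2.6.5 fixes the sampling: blood "will be obtained pretreatment, and at weeks 6, 12, 18, and 24 after the start of therapy". That gives four post-baseline values per patient. Section 2.8.3 rules out an interim efficacy analysis.

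**The concern.** An analyst who follows section 2.8.1 literally does not arrive at the synopsis endpoint. For a patient who stops giving samples early, the last observed value may come from Week 6, which is a different quantity from change at Week 24. The repeated-measures sentence does not say which visit or contrast decides. The velocity sentence lets the summary measure change on a condition with no number attached, no named decision-maker and no requirement that the decision be made blind. No hierarchy or multiplicity rule connects these.

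The trial has one biomarker endpoint and 60 patients, and its result is meant to support the design of a Phase III study (sections 1.2 and 1.4). If the Week 24 contrast, the last-value comparison and the slope disagree, the plan does not say which of them is the result. A positive finding on one of them could fairly be contested.

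**Working it through.** **Step 1: the plan's own power figure.** Inputs from section 2.8.2: IPF mean 8.51, control mean 0.47, SD 5.3, 30 per arm, alpha 0.05, taken as two-sided.

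- Difference = 0.5 × (8.51 − 0.47) = 4.02.
- Standard error = 5.3 × √(2/30) = 1.368.
- Noncentrality = 4.02 / 1.368 = 2.94, with 58 degrees of freedom.
- Power = 0.823, which reproduces 0.82.

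The text describes a reduction *to* 4.02. That would be a difference of 8.51 − 4.02 = 4.49 and a power of 0.897, so the stated power uses a reduction *by* 4.02. The 0.05 and 0.82 are correct for this single test.

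**Step 2: what happens if the test is not fixed.** The documents state no between-visit correlation, so a range of 0 to 0.9 is assumed. The paired power statement falls inside it. A 1.4 decrease with 30 patients and power 0.8, two-sided, needs an SD of differences of about 2.65. With SD 5.3 at both times this implies a correlation of 1 − 2.65²/(2 × 5.3²) = 0.875.

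For four independent tests at 0.05, the chance of at least one false positive is 1 − 0.95⁴ = 0.185. Because the visits are correlated, null trials were simulated: 20,000 per setting, 30 per arm, baseline plus four visits, normal outcome, complete data. The slope runs through baseline and all four visits. Each entry is the proportion of null trials with at least one p < 0.05, across the assumed correlations.

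| What may count as a win | Equal correlation | First-order autoregressive |
|---|---|---|
| Week 24 change only | 0.047–0.052 | 0.049–0.050 |
| Week 24 change or slope | 0.070–0.072 | 0.061–0.071 |
| Change at any of four visits | 0.154–0.160 | 0.135–0.160 |
| Change at any visit, or slope | 0.168–0.174 | 0.140–0.173 |

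The third row hardly moves under equal correlation, for a simple reason. Change scores share the same baseline, so their covariance is σ²(1 − ρ) and their variance is 2σ²(1 − ρ). Their correlation is therefore 0.5 whatever ρ is.

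**Step 3: the cost of keeping all visits in play.** With Bonferroni, each visit is tested at 0.05/4 = 0.0125. Power per visit at 30 per arm then falls from 0.82 to 0.64. Fixing one visit avoids that loss.

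**The case against.** The case for the plan has real weight. The synopsis does name Week 24. The phrase in section 2.7.1 can be read as the sampling schedule, which is less specific than the synopsis but does not contradict it. For any patient with a Week 24 sample, the last observed value is the Week 24 value, so the two measures part only for those without one. Sizing a trial with a t-test and analysing it with a repeated-measures model is common and does not by itself create a second primary test. Velocities are offered as a replacement for the tests, not as an extra one. A switch decided from blinded completion counts need not inflate the error at all. Retention is expected to be good: section 4.1.2 cites 39 of 44 patients completing procedures in earlier trials, and section 2.2 follows patients removed for adverse events to 24 weeks.

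These points rule out two stronger readings that a reader might draw. One is that the 0.05 is already broken. No section says that a win at any visit makes the trial positive, and a repeated-measures model with one Week 24 contrast or one global test would keep 0.05. The other is that the velocity switch is biased because dropout in IPF tracks outcome. The documents do not show that dropout is related to dityrosine, and that would in any case be a question of bias rather than of multiplicity.

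What stands is that section 2.8.1, the text that instructs the analyst, does not name the Week 24 contrast as decisive. It names another primary measure and permits an undefined change of method. The synopsis does not settle those points.

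**Conclusion.** The point holds as a gap in pre-specification: control at 0.05 is not assured. It is not shown to be lost. The size depends on how the open choice would be used. If the visit were picked after seeing results, the worst case is about 0.135 to 0.16 on change from baseline, rising to about 0.14 to 0.17 with a slope added. If only Week 24 change and slope compete, it is about 0.06 to 0.07. If Week 24 is fixed, it is 0.05.

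These rates rest on the assumed correlations of 0 to 0.9, normal outcomes and complete data. The 0.82 carries over to one fixed Week 24 t-test with SD 5.3 and 30 patients per arm. For change from baseline with SD 5.3 at each visit, the SD is 5.3 × √(2(1 − ρ)), which is no larger than 5.3 once ρ reaches 0.5.

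**What to change.** In section 2.8.1, name one primary test: the between-arm difference in change in dityrosine from baseline to Week 24, estimated from one repeated-measures mixed model with its terms and covariance structure stated, at two-sided 0.05. Label the comparisons at weeks 6, 12 and 18, the slope, the last-value analysis and the paired within-arm test as supportive and unable to establish a positive result. Delete the velocity option for the primary analysis. If it is kept, state its numerical trigger before unblinding and apply it to blinded completion counts only. Align sections 2.7.1 and 2.8.1 with the synopsis.

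The cost is wording. Sampling does not change, because blood is already drawn at all these visits, and neither does the sample size. What is given up is the freedom to change the primary analysis after the fact.
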